#### **V.2. Sensitivity Analysis for Noncompliance**

To assess the potential impact of non-compliance on the study outcomes, we will use a stratified-adjusted instrumental variable approach to estimate the average effect of spinal anesthesia vs general anesthesia on the primary endpoint for those who actually receive the assigned treatment (Matsui, 2005). Randomization assignment will serve as the instrumental variable because it is designed to be independent of unobserved confounders. The study population is assumed to include individuals who receive the assigned treatment (i.e. “compliers”), individuals who would receive general anesthesia regardless of their study assignment (“always users of general anesthesia”) and individuals who would always receive spinal anesthesia regardless of the study

assignment (“always users of spinal anesthesia”). The observed effect of treatment assignment on compliers is attenuated by the presence of “always users” (i.e. those who “cross over” if they are not assigned their preferred treatment). To correct for this attenuation, an estimated risk of the primary outcome among compliers will be calculated for individuals assigned to spinal anesthesia and general anesthesia separately, within each stratum (Greenland, 2000). The Mantel-Haenszel relative risk for compliers will be calculated as the ratio of the weighted summations of the adjusted risk over all strata. This estimate maximizes asymptotic efficiency even if the compliance rate varies across randomization stratum (Matsui, 2005).

## VI. Secondary Outcome Analyses

VI.1. 60 day mortality. This component of the primary endpoint will be assessed via site reports of deaths and at the day 60 telephone interview, and will be analyzed as a binary outcome using the MH method, stratified by sex, fracture type, and country. Patients who are unable to be assessed directly or by proxy at the 60-day telephone interview but who are known to be alive at later time points will be categorized as alive at day 60. Additional information on deaths prior to day 60 will be obtained via a National Death Index search for patients who were randomized at US sites with sufficient identifying information and for whom no follow-up at or beyond day 60 is available. The Breslow-Day test will be used to assess homogeneity of the RRs across strata.

VI.2. Ability to walk 10 feet without human assistance at 60 days post-randomization. This component of the primary endpoint will be analyzed as a binary outcome, using the MH test stratified by sex, fracture type, and country. Participants who died prior to completing the 60 day interview or had no informative answer to the ambulation assessment will be excluded from the analysis.

VI.3. New-onset delirium. This outcome will be determined by baseline and post-operative 3D CAM tests. Subjects will have a baseline 3D-CAM assessment prior to randomization and assessments on days 1, 2 and 3 post-surgery, with fewer assessments if discharged, withdrawn, or died prior to day 3. Only subjects with a baseline 3D-CAM assessment but no delirium will be included in the analysis. Subjects with a positive response on any post-surgery assessment will be classified as positive for new onset delirium. Subjects who had 1 or more post-surgery assessments with none positive for delirium will be classified as negative for this outcome. Subjects without any post-surgery 3D-CAM response will be excluded from this analysis. This binary outcome will be analyzed using the MH method, stratified by sex, fracture type, and country. The Breslow-Day test will be used to assess homogeneity of the RRs across strata.

VI.4. Days to hospital discharge. Days from randomization to hospital discharge or death, censored at post-randomization day 30, will be analyzed using a competing risk Cox regression model, adjusted for sex, fracture type, and country (Fine and Grey 1999). The cumulative incidence of hospital discharge will be compared between study arms. The proportional hazards assumption will be assessed using both survival graphs and formal statistical tests of zero slopes in the Schoenfeld residuals and if the proportional hazards assumption is violated, advanced techniques in survival such as incorporating time-dependent covariate effects will be applied (Grambsch and Therneau, 1994; Hess, 1995). Kaplan-Meier curves displaying times to discharge and accounting for competing death risk by study arm will be presented (Pepe and Mori 1993). The interaction between treatment and country will be tested in the Cox model and if the p-value for the interaction test is 0.2 or less, separate analyses by country will be presented.

## VII. Exploratory Analyses

For all exploratory outcomes, summary statistics (frequencies and percentages for categorical variables, means and standard deviations, or medians and IQRs for continuous variables, frequencies and median time to event for time-to-event variables) will be presented by arm. If there are sufficient events for analysis of binary outcomes, the Mantel-Haenszel relative risk, stratified by sex, fracture type, and country, will be estimated.

**VII.1. Inpatient major morbidity and mortality.** Study site personnel collected data on any of the below events occurring prior to death, discharge, or post-randomization day 30 via medical record review using outcome definitions listed in the REGAIN manual of procedures; additional information on postoperative acute kidney injury was obtained by comparison of site-reported pre-randomization creatinine vs peak post-operative creatinine values where available. Except where specified below, all morbidity and mortality endpoints will be analyzed as binary data.

- a. In-hospital death
- b. Myocardial infarction
- c. Troponin elevation without diagnosed myocardial infarction
  - i. Note: Information on peak postoperative troponin values was collected from REGAIN patients based on laboratory data obtained as a component of routine care. Information on isolated troponin elevation (i.e. without a diagnosis of myocardial infarction) will be reported for individuals not otherwise identified as having experienced a myocardial infarction.
- d. Non-fatal cardiac arrest
- e. Stroke
- f. Pneumonia
- g. Pulmonary embolus
- h. Pulmonary edema
- i. Unplanned postoperative intubation or need for mechanical ventilation
- j. Acute kidney injury
- k. Surgical site infection
- l. Urinary tract infection
- m. Any postoperative transfusion
- n. Any return to OR
- o. Need for critical care admission
- p. Fall within 12 hours of anesthesia

**VII.2. Time to first in-hospital ambulation after randomization (days).**

Time from randomization to first ambulation, censored at hospital discharge, will be compared using a Cox proportional hazards regression model, adjusted for sex, fracture type, country, and use of cane or walker at baseline. Kaplan-Meier curves displaying times to first ambulation by study arm will be presented.

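### The plain Kaplan-Meier curves planned for first in-hospital ambulation overstate the proportion who walk, because discharge or death before walking is not handled as a competing event

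*SAP*

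**What the plan says.** The heading of SAP section VII.2 confines the outcome to first ambulation in hospital, counted in days from randomization. The analysis is stated as "Time from randomization to first ambulation, censored at hospital discharge, will be compared using a Cox proportional hazards regression model", adjusted for the three general factors and for baseline use of a cane or walker. The display is stated as "Kaplan-Meier curves displaying times to first ambulation by study arm will be presented". Section VII.2 does not mention death.

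Three other places bear on this:

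- Section VII.1 lists "In-hospital death" among the collected events, so deaths before walking are possible and would be known.
- The opening of section VII promises, for all exploratory outcomes, "frequencies and median time to event for time-to-event variables) will be presented by arm".
- Section VI.4, on days to hospital discharge, takes a different route. That outcome "will be analyzed using a competing risk Cox regression model, adjusted for sex, fracture type, and country", cumulative incidence is compared between arms, and the curves are to allow for death as a competing risk.

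**The concern.** Kaplan-Meier treats a censored patient as having the same future chance of the event as those still under observation. That does not fit here. After discharge or death without walking, the chance of a first in-hospital walk is zero. One minus Kaplan-Meier then answers a hypothetical question: what proportion would walk if nobody left or died first. It does not give the proportion who walk in hospital.

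What is at stake is how the curves compare the arms. Section VI.4 tests time to discharge between arms, so the SAP itself allows that the event used here for censoring may differ by treatment. If one arm has more patients who leave or die without walking, plain Kaplan-Meier curves need not show it. The SAP accounts for competing death in its neighbouring in-hospital time outcome and gives no reason for not doing so here.

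**Working it through.** The SAP states no walking rate, unwalked-discharge rate, death rate or event count for this outcome. There is no figure to reproduce, and **every rate below is an assumption** used to find the direction and plausible range.

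**Daily model.** Let *h* be the daily chance of first walking among patients in hospital who have not yet walked. Let *c* be the daily chance of discharge without walking, applied from day 3, and *m* the daily chance of death, applied from day 1. With S(0) = 1:

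- S(d) = S(d−1) × (1−h)(1−c)(1−m), still in hospital and not walked
- F(d) = sum over k ≤ d of S(k−1) × h, the true cumulative proportion walking in hospital
- 1−KM(d) = 1 − (1−h)^d, what Kaplan-Meier gives when discharge and death are censored

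**Middle scenario in full** (h = 0.30, c = 0.04, m = 0.005):

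- S(1) = 0.70 × 0.995 = 0.6965 and S(2) = 0.6965² = 0.48511
- F(2) = 0.30 + 0.6965 × 0.30 = 0.50895
- F(3) = 0.50895 + 0.48511 × 0.30 = 0.654, against 1−KM(3) = 1 − 0.70³ = 0.657
- From day 3, S shrinks each day by 0.70 × 0.96 × 0.995 = 0.66864, so F tends to 0.50895 + 0.48511 × 0.30 / (1 − 0.66864) = 0.948, while 1−KM tends to 1

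**Three scenarios, 1−KM against true proportion:**

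| Scenario (h, c, m) | Day 3 | Day 7 | Day 14 | Day 30 |
|---|---|---|---|---|
| Low (0.40, 0.01, 0.002) | 0.784 vs 0.783 | 0.972 vs 0.966 | 0.999 vs 0.991 | 1.000 vs 0.992 |
| Middle (0.30, 0.04, 0.005) | 0.657 vs 0.654 | 0.918 vs 0.889 | 0.993 vs 0.945 | 1.000 vs 0.948 |
| High (0.25, 0.10, 0.01) | 0.578 vs 0.573 | 0.867 vs 0.796 | 0.982 vs 0.848 | 1.000 vs 0.851 |

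The gap is 0.1 to 0.5 points at day 3 and 0.8 to 13.4 points at day 14.

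**Dependence on when unwalked discharge begins.** Suppose it can occur from day 1, with h = 0.35 and a constant competing rate set so that 5%, 10% or 20% never walk in hospital. Then 1−KM at day 3 is 72.5%, against a true 71.1%, 69.5% or 65.8%. The small early gap therefore depends on unwalked discharge starting later.

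**Death alone.** With h = 0.30, no unwalked discharge, and m = 0.002, 0.005 or 0.01, the true day-30 proportion is 0.995, 0.988 or 0.977 against 1−KM of 1.000. The gap is 0.5 to 2.3 points. In the middle and high scenarios, unwalked discharge drives most of the bias.

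**Can a difference between arms be hidden?** Give every group the same h = 0.30 and m = 0.005, and let c be 0.02, 0.04 or 0.08. The true day-30 proportions walking are 0.967, 0.948 and 0.914. 1−KM is 1.000 in all three, so a true spread of 5.3 points (96.7 − 91.4) would not appear.

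**Patients who cannot walk at all.** The daily model gives every patient the same walking chance. A simulation of 200,000 patients per setting relaxed this: 5%, 10% or 15% never able to walk, 1%, 2% or 3% dying, a daily walking chance of 0.45 for the rest, and a stay of 3 days plus a Poisson count with mean 3 for those who survive.

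| Never able to walk / dying | Day 3, 1−KM vs true | Day 7 | Day 10 |
|---|---|---|---|
| 5% / 1% | 0.791 vs 0.791 | 0.935 vs 0.907 | 0.948 vs 0.909 |
| 10% / 2% | 0.750 vs 0.750 | 0.885 vs 0.858 | 0.897 vs 0.860 |
| 15% / 3% | 0.709 vs 0.709 | 0.837 vs 0.811 | 0.848 vs 0.813 |

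The direction is the same. The day-10 gap is 3.5 to 3.9 points, and 1−KM does not approach 100% by then.

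**The case against.** **The Cox model is not wrong.** A reader might infer that censoring at discharge or death invalidates the hazard ratio. It does not. With competing events censored, Cox regression estimates the cause-specific hazard ratio: the relative rate of first walking among patients in hospital who have not yet walked. That is an accepted target. Making a Fine-Gray model the main analysis would be a choice of estimand, with its own drawback: it keeps patients who left without walking in the risk set, so its ratio mixes recovery with discharge practice. Section IV already anticipates differences in health care between the two countries. This objection stands.

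**The SAP does not say that deaths are ignored.** It is silent. Section VII.3 counts death as a category of discharge location, so discharge in VII.2 may be meant to include death. That is fair, but on that reading deaths are simply censored, and the curve still does not treat them as competing events.

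**The number who walk is reported anyway.** Section VII promises frequencies and median times by arm. This lessens the harm. It does not correct the curve, and it does not separate patients who left without walking from those who died.

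**The size is assumed.** This stands in full. A reader might infer that the curves must climb to 100%, or that gaps of 20 points are to be expected. Those results need one walking rate shared by all patients together with a high assumed share who never walk, and the SAP supports neither.

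**Section VI.4 is not an exact template.** There discharge is the event and death the only competing event. It shows that the SAP accounts for competing death in a curve, but it does not settle the model for VII.2.

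**Conclusion.** The point holds for the curves and is minor. As planned, one minus Kaplan-Meier overstates the cumulative proportion who walk in hospital; drawn as the proportion not yet walking, the curve is too low. It can also conceal a difference between arms in discharge or death without walking.

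The direction follows from the definition of the outcome. The size rests wholly on assumed rates: about 1 to 13 points by day 14 in the daily model, and 3.5 to 3.9 points at day 10 when some patients can never walk. If unwalked discharge starts only around day 3, the bias up to then is 0.5 points or less, and a median reached in the first two to three days would hardly move.

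The documents do not support the stronger reading that the planned Cox comparison is invalid. Its hazard ratio is usable but does not by itself say which arm gets more patients walking. The outcome is exploratory, so the primary and secondary analyses are untouched.

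**What to change.** In section VII.2:

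- State how in-hospital death before walking is handled, and whether discharge includes death.
- Replace the Kaplan-Meier curves with Aalen-Johansen cumulative incidence of first ambulation by arm, taking in-hospital death and discharge without walking as competing events. This agrees with the allowance for competing death in the section VI.4 curves.
- Keep the Cox model with its listed covariates, and label the result a cause-specific hazard ratio.
- Report for each arm the number discharged without walking and the number who died without walking.
- Optionally add a Fine-Gray hazard ratio as supportive, noting that it also reflects discharge practice.

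The cost is a few lines of SAP text, one changed figure and one extra row or two in a table. Competing-risk methods are already planned for section VI.4. Section VII.1 already lists in-hospital death, and VII.2 itself requires discharge and first-ambulation times, so no new data should be needed.

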**VII.3. Discharge location.**

The location is a categorical outcome with five categories: (i) home and independent living retirement home; (ii) nursing home; (iii) rehabilitation or acute care hospital; (iv) other; and (v) death. If there are sufficient subjects in each category, this outcome will be analyzed using a multinomial logistic regression, adjusted for sex, fracture type, and country.

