## **IV. General Principles**

All analyses (primary, secondary, exploratory) will adjust for the 2 binary stratification factors, namely sex, fracture type (intracapsular, extracapsular), and country (U.S., Canada sites). Sex, fracture type, and site were the original stratification factors for randomization assignment, but with 46 participating sites, some with very few enrolled subjects, it will not be possible to include site in the stratified analysis. Because there might be systematic differences in health care and insurance use between Canada and U.S. sites, we will add country as an additional stratification factor. We will perform descriptive analyses of results by site to see whether there appear to be any major site-specific effects. Analyses will follow a modified intention-to-treat principle, with sensitivity analyses performed to assess the potential impact of missing values and noncompliance. Subjects who had randomization codes generated due to purely technical errors in operating the database will be excluded from any analysis. Subjects who died before receiving either study treatment will also be excluded from any analysis. Subjects randomized and later found not to meet eligibility criteria will be included in the primary analysis to avoid potential bias due to differential assessment of eligibility. Sensitivity analyses excluding these subjects will be conducted. Subjects who were randomized into the wrong stratum will be analyzed as per-randomization strata. All analyses will use 2-sided tests and an overall significance level of 0.05 as the threshold for statistical significance. We will report nominal p-values for all analyses.

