#### VII.4. Additional 60-day outcomes.

- a. Time to death: Days from randomization to death, censored at day 60, will be compared using a Cox proportional hazards regression model, adjusted for sex, fracture type, and country. Kaplan-Meier curves displaying times to death by study arm will be presented. For those with missing data on vital status at day 60, we will search the National Death Index. If death month and year are available but the day is missing, day 15 will be used as an estimate of the date.
- b. Worsened walking ability: Subjects are coded as “worsened” if at day 60 they needed a level of assistance in walking greater than prior to surgery, or if they could not walk at all, or if they died prior to day 60. Specifically, those who could walk without human assistance at baseline are considered to have worsened if at day 60 they required assistance to walk (e.g. cane, walker or human assistance), could not walk at all, or died prior to day 60; Those who required a cane or walkers at baseline are considered worsened if they needed human assistance to walk or could not walk at day 60, or if they died prior to day 60.
- c. Death or transition to institutional residence at 60 days: We will ask patients their residence locations before hospital admissions. We will also assess a location of residence on or around post-randomization day 60 via blinded telephone interview with the patient or their proxy. The analysis for this endpoint will include all individuals who were admitted from home or retirement home. Individuals who died before 60 days or reported change of residence location (including nursing home, acute rehabilitation, acute care hospital, and other) at the 60 day interview will have “positive” responses; individuals remained at home or independent living retirement home will have “negative” responses. Subjects without a valid admission location, or a 60-day vital status and valid residence location, will be excluded from the analysis. This outcome will be analyzed as a binary variable.

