#### **VIII. Subgroup Analyses**

We will evaluate treatment difference in the subgroups defined by the following stratification variables:

- a. Sex: Male vs. Female, defined as per stratification
- b. Fracture type: Femoral neck vs intertrochanteric/subtrochanteric, defined as per stratification
- c. Country of enrollment: Canada vs US
- d. Need for assistive devices to ambulate prior to fracture: present vs. absent
- e. Age category: “oldest old” (85 years and over) vs all others
- f. History of Alzheimer’s disease or other dementia: present vs absent
- g. History of chronic obstructive pulmonary disease or asthma: present vs absent
- h. History of coronary artery disease or prior myocardial infarction: present vs absent
- i. Community residence prior to fracture: home or independent living retirement home vs nursing home, rehabilitation or acute care hospital vs other.

The first step will be to test for interaction between treatment and variable defining the subgroups. Analysis within subgroups will be performed for any variable showing an interaction yielding a p-value of 0.20 or less. Subgroup analyses will be analyzed similarly as for primary analysis.

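### The exploratory discharge-location model (SAP VII.3) leaves out pre-fracture residence, which dilutes and blurs the nursing-home contrast without biasing it

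*SAP*

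**What the plan says.** Section VII.3 defines the outcome by destination only: "i) home and independent living retirement home; (ii) nursing home; (iii) rehabilitation or acute care hospital; (iv) other; and (v) death". If every category has enough subjects, "this outcome will be analyzed using a multinomial logistic regression, adjusted for sex, fracture type, and country". The section names no population, so the default in section IV applies: "Analyses will follow a modified intention-to-treat principle". Nothing in VII.3 separates a return to the previous residence from a new placement.

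The SAP shows elsewhere that origin is known and that it varies:

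- VII.4.c records it: "We will ask patients their residence locations before hospital admissions".
- VII.4.c also uses it to define who is analysed: "The analysis for this endpoint will include all individuals who were admitted from home or retirement home".
- Section VIII, item i, lists institutional origins as subgroup levels: "Community residence prior to fracture: home or independent living retirement home vs nursing home, rehabilitation or acute care hospital vs other".

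Neighbouring outcomes take account of where the patient started. Time to first ambulation (VII.2) is "adjusted for sex, fracture type, country, and use of cane or walker at baseline". Worsened walking (VII.4.b) is defined against walking before surgery, and the disability score (VII.4.d) is adjusted for its baseline value.

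**The concern.** For someone who lived in a nursing home before the fracture, discharge to a nursing home is the expected return to the starting point. For someone who lived at home it is a new placement. VII.3 counts both as the same event and gives the model no means of telling them apart.

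Patients whose destination is largely settled by their origin add many nursing-home outcomes that carry little information about anesthesia type. They move the estimated contrast towards no effect. A reader who sees a nursing-home odds ratio also cannot tell how far it reflects new placement.

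The subgroup plan does not fill the gap, because its within-group results are conditional: "Analysis within subgroups will be performed for any variable showing an interaction yielding a p-value of 0.20 or less". Those analyses are also modelled on the primary analysis. The general text of section VII promises summaries by arm, not by origin.

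**Working it through.** The SAP states no rate, sample size or power for this outcome, so there is no figure of its own to reproduce. The check has a textual part, set out above, and an illustration of size.

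**Inputs from the SAP.** Five destination categories; a multinomial model with sex, fracture type and country; no restriction by origin; two-sided 0.05.

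**Assumed inputs (none is in the SAP).** Home is the reference category. Home dwellers go to a nursing home in 25% vs 20%, home in 35% vs 40%, and elsewhere in 40% in both arms. Prior nursing home residents go back there in 90% and home in 0%, in both arms. They make up a share p of patients. Covariates are ignored.

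**Formulas.** In each arm:

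- Nursing home = (1 − p) × home-dweller risk + p × 0.90
- Home = (1 − p) × home-dweller chance of going home
- Odds ratio (OR) = (nursing home / home in arm A) ÷ (nursing home / home in arm B)

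In home dwellers alone, OR = (0.25/0.35) ÷ (0.20/0.40) = 1.429, log 0.357.

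| p | Arm A: nursing home / home | Arm B: nursing home / home | OR | log OR | Share of 0.357 |
|---|---|---|---|---|---|
| 5% | 0.2825 / 0.3325 | 0.2350 / 0.3800 | 1.374 | 0.318 | 89% |
| 10% | 0.3150 / 0.3150 | 0.2700 / 0.3600 | 1.333 | 0.288 | 81% |
| 15% | 0.3475 / 0.2975 | 0.3050 / 0.3400 | 1.302 | 0.264 | 74% |

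At p = 10%, returns make up 0.10 × 0.90 / 0.315 = 29% of nursing-home discharges in arm A.

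**Sensitivity.** Let 2% of prior residents be coded as going home, and let home dwellers go home in 30% vs 35%. At p = 10% the OR falls from 1.46 to 1.36, again 81% on the log scale.

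**Cruder contrast.** If nursing home is set against every other destination, the home-dweller OR of 1.33 becomes 1.28, 1.24 and 1.21 (86%, 76% and 67% of the log OR). That overstates the loss for the planned model, because a multinomial model contrasts specific categories.

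**Precision.** A separate binary illustration assumes 800 per arm, home-dweller risks of 30% vs 24%, and 95% return in both arms:

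| Prior residents | Power, all patients | Power, home-admitted only |
|---|---|---|
| 5% | 0.70 | 0.75 |
| 10% | 0.63 | 0.73 |
| 20% | 0.50 | 0.68 |

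Under these inputs, including the prior residents lowers power even though it adds patients.

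**The case against.** The strongest reply is that VII.3 is sound as written. Its title is discharge location, and section I lists health care utilization among the domains covered. Where all randomized patients go after the acute stay is a coherent question, it follows the modified intention-to-treat default, and the all-patient effect is a valid marginal effect. Being closer to 1 than the effect in a subset does not make it wrong. This stands, and it is why the all-patient summary should stay.

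A reader might infer that VII.3 contradicts VII.4.c because the populations differ. The text does not support that. VII.4.c is a transition outcome and needs people who can still make the transition; VII.3 is not defined as a change. Nor would a shared population make the two directly comparable. One is a binary composite with death at about day 60, and the other has five categories at discharge.

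A reader might also infer bias between arms. Randomization balances origin on average, so neither bias nor an inflated type I error follows.

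Two further objections hold. Every input to the size is assumed, and at a 5% share of prior residents the loss is modest. Restricting the model also removes randomized patients, including those who die in hospital, so adjustment deserves first consideration.

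The replies do not explain why a collected and strongly predictive baseline state is left out of this model when the neighbouring outcomes use theirs.

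**Conclusion.** The point holds as a minor one. VII.3 codes returns and new placements alike and makes no use of origin. The consequences are dilution, lost precision and an unclear reading of the nursing-home category. Under the stated assumptions the nursing-home-versus-home log OR keeps about 89%, 81% or 74% of its home-dweller value at 5%, 10% or 15% prior residents. The share admitted from institutions decides how much this matters, and the SAP does not give it. The other contrasts in the model were not quantified.

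The outcome is exploratory, its model is run only if categories are large enough, and no primary or secondary result depends on it. The documents do not support calling the planned comparison invalid.

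**What to change.** Amend VII.3 as follows:

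1. Keep the all-patient frequency table of discharge location by arm.
2. Add pre-fracture residence to the multinomial model as a covariate: community (own home or independent-living retirement home) versus institution. State where origins coded as other, or missing, are placed.
3. If cells for institutional patients are too sparse, as they would be if almost none go home, fit the model in community-admitted patients, the population of VII.4.c. Fix the sparseness rule before unblinding.
4. Add a table of origin by destination, by arm.

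The cost is SAP wording and one table, since origin is already collected. The downside is small: one more covariate or, under the fallback, patients admitted from institutions appear only descriptively.
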